3.1.6 Prior and concomitant medication

Medications taken by any subject at any time during the study will be coded using the Anatomical Therapeutic Chemical (ATC) classification system within the World Health Organisation (WHO) Drug Dictionary.

Medications will be categorised for analysis according to their onset and end dates as follows:

- Prior medications:
 - end date \leq date of first dose of IP
- Concomitant medications during on-treatment period:
 - end date $>$ date of first dose of IP and start date \leq minimum (date of last dose of IP + 33 days, date of death, date of study withdrawal), or
 - end date ongoing and start date \leq minimum (date of last dose of IP + 33 days, date of death, date of study withdrawal)
- Concomitant medications during post-treatment period (for subjects still being followed up then):
 - start date $>$ date of last dose of IP + 33 days

Background COPD medication (i.e., triple therapy) will be classified as a ‘COPD medication at baseline’ if it started on or prior to randomisation and ongoing after randomisation.

If the medication record has a completely missing onset date, the subject will be assumed to have been on the medication on the date of the first study procedure. If the medication record has a partially missing onset date (month/year or year only) which is the same as that for the end of IP treatment, it will be assumed to have started on-treatment. If the medication record has a partially missing onset date (month/year or year only) which is the same as that for the start of IP treatment, it will be assumed to have started before treatment.

If the medication record has a completely missing end date, the subject will be assumed to have been on the medication on the date of study completion or withdrawal. If the medication record has a partially missing end date (month/year or year only) which is the same as that for start of IP treatment, it will be assumed to have ended on-treatment. If the medication record has a partially missing end date (month/year or year only) which is the same as that for end of IP treatment, it will be assumed to have ended post-treatment.

3.1.7 Definition of subgroups

The following subgroups are defined for the purpose of primary efficacy subgroup analysis and for secondary efficacy subgroup analysis (SGRQ and pre-BD FEV₁ only):

- Screening blood eosinophils group: <150/μL, ≥150/μL
- Baseline blood eosinophils group: <150/μL, ≥150 to <300/μL, ≥300/μL
- Baseline clinic visit FeNO group 1: <25ppb, ≥25ppb
- Baseline clinic visit FeNO group 2: <25ppb, ≥25 to <50ppb, ≥50ppb
- Age category at study entry: ≥40 to <65 years, ≥65 to <80 years
- Gender: Male, Female
- Race: White, Black or African American, Asian, Other
- Baseline Body Mass Index (BMI): <25 kg/m², ≥25 to 30 kg/m², ≥30 kg/m²
- Chronic bronchitis at baseline (presence or absence of chronic bronchitis as recorded in RESHISTE module of the eCRF)
- Emphysema at baseline (presence or absence of emphysema as recorded in RESHISTE module of the eCRF)
- COPD characteristics at baseline (No emphysema or chronic bronchitis, Only emphysema, Only chronic bronchitis, Emphysema and chronic bronchitis as recorded in RESHISTE module of the eCRF)
- Prior severe exacerbation at randomization as recorded in eCRF: Yes, No
- Prior exacerbation counts recorded at randomisation as recorded in IWRS: 2, ≥3
- Baseline smoking status: Current, Former
- Baseline smoking status: ≥baseline median number of pack years, <baseline median number of pack years

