5.1 Inclusion Criteria

Subjects are eligible to be included in the study only if all the following inclusion criteria and none of the exclusion criteria apply:

Informed consent:

- 1. Provision of signed and dated, written informed consent form prior to any mandatory study specific procedures, sampling, and analyses.
- 2. Provision of signed and dated written addendum to informed consent form for sputum/nasal sub studies prior to collection of sputum/nasal samples (if applicable).
- 3. Provision of signed and dated written genetic informed consent prior to collection of optional samples for genetic analysis (if applicable).

The ICF process is described in Appendix A 3.

Age:

4. Female or male subjects aged \geq 40 to 80 years inclusive at the time of enrolment (Visit 1).

Type of subject and disease characteristics:

- 5. History of moderate to very severe documented physician-diagnosed COPD for at least 12 months prior to enrolment with a post-bronchodilator FEV1/FVC<0.70 and a post-bronchodilator FEV₁ \geq 20% and \leq 80% of predicted normal value at Visit 2 (or Visit 1 if Visit 1 and 2 are combined).
- 6. History of at least 2 documented moderate to severe COPD exacerbations, within 2 to 52 weeks prior to enrolment (Visit 1) or re-screening Visit 1. See Section 4.1 for required source documentation for this inclusion.
 - A moderate COPD exacerbation is defined as an exacerbation that required treatment with systemic corticosteroids for at least 3 days duration (or 1 injection of depot formulation) and/or antibiotics.
 - A severe COPD exacerbation is defined as an exacerbation that required hospitalization (defined as an inpatient admission ≥24 hours in the hospital, in an observation area, the emergency department or other equivalent healthcare facility depending on the country and healthcare system).
 - Prior use of antibiotics alone does not qualify as a moderate exacerbation unless the antibiotic was specifically prescribed for the treatment of worsening COPD symptoms.
 - Previous exacerbations should be confirmed to have occurred while patient
 was on stable triple (ICS/LABA/LAMA) background therapy for COPD and
 not as a result of a step down in therapy, i.e. change from triple to dual
 therapy.

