3. PRIMARY AND SECONDARY VARIABLES

3.1 General definitions

3.1.1 Age calculation

Age will be derived from the date of informed consent - date of birth, rounded down to the nearest integer. For subjects in countries where date of birth is not recorded, the age as recorded in the eCRF will be used.

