4.2 Analysis methods

4.2.1 Subject disposition, demography, and baseline characteristics

Subject disposition will be summarised using the all subjects analysis set. The number of enrolled subjects and those not randomised (and reason) will be summarised. The number and percentage of subjects within each treatment group will be presented by the following categories; randomised, received IP, did not receive IP (and reason), completed treatment, discontinued treatment (and reason), completed study (subjects who completed IP and study, and subjects who discontinued IP but completed study assessments), and discontinued study (including reason). All randomised subjects will be used as the denominator in percentage calculations for the applicable categories above.

Subject recruitment by country and centre will also be summarised for subjects in the FAS.

Disposition will also be provided for the number and percentage of randomised subjects who consented separately to participate in the optional sub-studies (e.g. DNA sampling, sputum and nasal lining fluid/epithelial cells sub studies).

The number of subjects in each of the analysis sets defined in Section 2.1 will be presented.

The number and percentage of subjects, who discontinued IP, but remained in the study will be presented by treatment group and option of follow up (Section 1.2) at each scheduled timepoint.

Kaplan-Meier plots will be produced summarising separately the time (in days) to premature discontinuation of IP and withdrawal from the study. In both cases, subjects without the premature event will be censored at Week 52.

Demographic data such as age, gender, and race will be summarised by treatment group for subjects in the FAS. All subgroups as defined in Section 3.1.7 will be summarised by treatment group for subjects in the FAS. In addition, the screening blood eosinophil category $\geq 150/\mu\text{L}$ will be further categorised as $\geq 150 - 300/\mu\text{L}$, and $\geq 300/\mu\text{L}$ and summarised by treatment group.

Various baseline characteristics will also be summarised for the FAS by treatment group, which include respiratory disease history, subject characteristics (weight, height and BMI), nicotine use and consumption, baseline lung function (pre- and post-BD FEV₁ (L), FEV₁ (% PN), FVC (L), FVC (% PN), and FEV₁/FVC). The number of historic COPD exacerbations will be plotted.

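### SAP 3.1.7 has no age category for eligible subjects aged 80, so as written they have no level in the exploratory age-subgroup models or in the baseline age rows

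*SAP*

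**What the plan says.** Protocol 5.1, criterion 4, sets eligibility at "40 to 80 years inclusive at the time of enrolment". SAP 3.1.1 fixes how age is computed: "Age will be derived from the date of informed consent - date of birth, rounded down to the nearest integer". SAP 3.1.7 then lists the subgroup factors, among them:

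- Age: "Age category at study entry: ≥40 to <65 years, ≥65 to <80 years".
- BMI: "Baseline Body Mass Index (BMI): <25 kg/m², ≥25 to 30 kg/m², ≥30 kg/m²".
- Eosinophils, two factors: "Baseline blood eosinophils group: <150/μL, ≥150 to <300/μL, ≥300/μL" and "Screening blood eosinophils group: <150/μL, ≥150/μL".

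These factors are used in four places. SAP 4.2.4.3 fits one negative binomial model per factor for the primary endpoint, SAP 4.2.5.5 does the same by MMRM for pre-BD FEV1, and SAP 4.2.5.6 for SGRQ total score; each section bases the analysis on the FAS. SAP 4.2.1 tabulates every 3.1.7 subgroup by treatment group, again for the FAS.

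SAP 4.2.1 adds one cut that is not in 3.1.7. The upper screening-eosinophil category "will be further categorised as" 150 to 300 and 300 or more, for a summary by treatment group.

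Protocol 9.5.3 leaves all subgroup details to the SAP, so no other text supplies the missing age category.

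**The concern.** A subgroup factor should place every eligible subject in exactly one level. The age factor does not: its upper limit excludes an age that the protocol includes. A subject aged 80 meets the entry criterion and is not a protocol deviation, yet has no value for the factor. In a model that contains the age main effect and the treatment-by-age interaction, a record with a missing factor is normally left out. The fitted set would then be smaller than the FAS, and those left out would all come from the oldest end of the population. The only exclusion that the three model sections provide for is an imbalanced subgroup that causes convergence problems, which is a different situation.

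What is at stake is modest: an unexplained shortfall in three exploratory models, a baseline table whose age rows do not sum to the FAS, and a repair that would look like a post hoc choice if made after unblinding.

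**Working it through.** There is no stated figure to reproduce. The check is whether each possible value falls in exactly one category as written.

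**Age** (Protocol 5.1; SAP 3.1.1; SAP 3.1.7)

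- Eligible whole-number ages: 80 − 40 + 1 = 41 values.
- Lower category, 40 to 64: 64 − 40 + 1 = 25 values.
- Upper category, 65 to 79: 79 − 65 + 1 = 15 values.
- Covered: 25 + 15 = 40. Uncovered: 41 − 40 = 1, namely age 80. No age is in two categories.
- Because age is rounded down, the single uncovered value stands for a full year of life.

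**Other numeric factors**

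- BMI, tested from 10.0 to 60.0 in steps of 0.1, with the upper limit of the middle group read as inclusive: 30.0 is the only value in two groups, and there are no gaps.
- Eosinophil factors in SAP 3.1.7, tested from 0 to 2000/μL: no gaps and no overlaps, for either the baseline or the screening factor. A count of 300 belongs only to the top baseline group.
- Three-level FeNO factor, tested from 0 to 299 ppb: no gaps and no overlaps.
- Descriptive screening split in SAP 4.2.1, with the dash read as inclusive: 300 is the only value in two groups.

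**How many subjects**

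The planned number randomised is 338 (SAP 1.3). The share aged 80 at entry is not given, so it is an assumption:

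- 0%: 338 × 0 = 0
- 0.5%: 338 × 0.005 = 1.7
- 1%: 338 × 0.01 = 3.4
- 2%: 338 × 0.02 = 6.8
- 3%: 338 × 0.03 = 10.1

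The range is therefore 0 to about 10. It is an upper guide for the FEV1 and SGRQ models, because SAP 4.2.5.5 (whose model SAP 4.2.5.6 follows) already requires a baseline and at least one later value.

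**After correction**

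- Age with a top category of 65 to 80: 25 + 16 = 41, so every eligible age is in exactly one category.
- BMI with a middle group of ≥25 to <30: every tested value is in exactly one group.

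**The case against.** Four things can be said on the other side.

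First, the SAP never states that a subject without a category is excluded. It says that the analyses are on the FAS, and a programmer might well put an 80-year-old in the older group. That is fair: loss of subjects is what the category definition implies, not something the SAP announces. But the definition and the FAS statement then conflict, and the plan should settle this rather than leave it to programming.

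Second, there may be no such subjects. This stands; the range has to start at zero.

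Third, SAP 4.2.4.3 calls the primary-endpoint subgroup analyses exploratory and says that the study was not designed or powered for them, and SAP 4.1.2 treats all additional p-values as nominal. This also stands and limits the importance of the point.

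Fourth, a reader might infer more from the other boundaries than they support:

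- That subjects with an eosinophil count of 300 sit in two groups in the subgroup models. They do not. Both factors in SAP 3.1.7 are exhaustive and mutually exclusive; the overlapping wording is in SAP 4.2.1 and feeds only a descriptive summary.
- That a BMI of 30 puts a subject in two groups or removes the subject. A categorical covariate takes one value per subject, so nobody is lost or counted twice. The open question is only which label an exact 30 receives. The neighbouring three-level FeNO and eosinophil factors exclude the upper limit of their middle groups, which suggests the intended reading. The documents give no basis for a count of subjects at exactly 30.
- That several subgroup factors are therefore analysed on the wrong subjects. Only age can lose anyone.

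**Conclusion.** The point holds for age. Protocol criterion 4 and SAP 3.1.7 disagree about age 80, and as written the SAP gives those eligible subjects no level in three age-subgroup models specified on the FAS, nor a row in the baseline age summary.

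The size is 0 to about 10 of 338 subjects, assuming that between 0% and 3% are 80 at entry; the documents can neither narrow this range nor rule out zero. The consequence also assumes that a subject with no factor level is left out of the model, which is usual software behaviour but is not stated in the SAP.

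The BMI boundary at 30 and the eosinophil split in SAP 4.2.1 are editorial matters that change no analysis set. The primary analysis, sample size, power and type I error are unaffected. This is a minor correction.

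**What to change.** In SAP 3.1.7, change the top age category to ≥65 to ≤80 years, or to ≥65 years. Either covers every eligible age.

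As clean-up in the same edit:

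- SAP 3.1.7: write the middle BMI group as ≥25 to <30 kg/m².
- SAP 4.2.1: write the descriptive screening-eosinophil split as ≥150 to <300/μL and ≥300/μL, which matches the baseline factor in SAP 3.1.7 and the enrolment bands in Protocol 4.1.

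Leave the eosinophil factors in SAP 3.1.7 as they are. The cost is a few characters in the SAP, with no change to data collection, sample size or the primary analysis. It should be made before unblinding, so that the placing of 80-year-olds is pre-specified.

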3.2 Derivation of efficacy variables

3.2.1 Primary endpoint

3.2.1.1 The annual rate of COPD exacerbations

The annual rate of COPD exacerbations over 52 weeks will be used as the primary efficacy variable. A COPD exacerbation will be defined as a change in the subject's usual COPD symptoms that is beyond normal day-to-day variation, is acute in onset, lasts 2 or more days (or less if the worsening is so rapid and profound that the treating physician judges that intensification of treatment cannot be delayed), and may warrant a change in regular medication and leads to any of the following:

- Use of systemic corticosteroids for at least 3 days; a single depot injectable dose of corticosteroids will be considered equivalent to a 3-day course of systemic corticosteroids
- Use of antibiotics for at least 3 days
- An inpatient hospitalisation due to COPD (defined as an inpatient admission ≥ 24 hours in the hospital, in an observation area, the emergency department or other equivalent healthcare facility depending on the country and healthcare system)
- Results in death

All protocol-defined COPD exacerbations must fulfil the criteria above and be supported either by an eDiary alert, with duration recorded in the eCRF or by an investigator justification. Symptoms will be recorded in the eCRF only if an eDiary alert was not generated. All COPD exacerbations recorded in the eCRF, including investigator justified exacerbations, will be included in analyses provided they are not within 7 days of a prior exacerbation as defined below.

A COPD exacerbation will be considered **severe** if it results in at least 1 of the following:

- Hospitalisation due to the COPD exacerbation
- The subject being admitted for ≥ 24 hours to an observation area, the emergency department, or other equivalent healthcare facility (depending on the country and healthcare system) for the COPD exacerbation
- Death related to COPD or COPD exacerbation

A COPD exacerbation that does not meet the requirements to be classified as severe will be considered **moderate** if it results in at least one of the following:

- Use of systemic corticosteroids and/or antibiotics for at least 3 days
- A single depot injectable dose of corticosteroids, which will be considered equivalent to at least 3-day course of systemic corticosteroids

In order to calculate the number of exacerbations experienced by a subject during the treatment period, the following rule will be applied:

The start of an exacerbation is defined as the start date of systemic corticosteroids or antibiotic treatment or hospital admission, whichever occurs earlier, and the end date is defined as the last day of systemic corticosteroids or antibiotic treatment or hospital discharge, whichever occurs later.

A single depot injectable dose of corticosteroids will be considered equivalent to at least 3-day course of systemic corticosteroids. The corresponding stop date for this treatment will consequently be determined as the date of administration plus 2 days. If multiple treatments are prescribed for the same exacerbation, the earliest start date and the latest stop date will be used. For a severe COPD exacerbation with no documented corticosteroid or antibiotics treatment, hospitalization admission/discharge dates, or emergency visit date will be used as start/stop dates.

In the event of partial or missing start or stop dates recorded in the eCRF for systemic corticosteroids, antibiotic treatment, or hospital admission, the partial or missing start or stop dates will be imputed based on the overall exacerbation start and end dates as specified above.

Two or more exacerbations with the same start date and end date will be counted as one exacerbation for the purposes of calculating the number and duration of exacerbations for a subject. In such cases, severity will be the maximum severity of the events. In the case that one or more exacerbations are recorded as starting or ending during another exacerbation, these will be counted as one exacerbation, using the earliest exacerbation start date and the latest exacerbation stop date to calculate duration.

Additional systemic corticosteroid treatments, emergency room visits requiring use of systemic corticosteroids, or inpatient hospitalisation due to COPD occurring during an exacerbation should not be regarded as a new exacerbation. In order to be counted as a new exacerbation it must be preceded by at least 7 days in which none of the exacerbation criteria are fulfilled, i.e. if the end date of the first exacerbation and the start date of the second exacerbation are ≤ 7 days apart, then these will be counted as one exacerbation.

The maximum follow-up time for exacerbations for a subject is approximately 52 weeks; defined under the primary estimand as the time from randomisation to the date of Visit 16 (EOT), regardless of whether subjects remain on randomised treatment. For a subject lost to follow-up or prematurely withdrawing from the study prior to Visit 16 (EOT), this will be defined as the time from randomisation to the time point after which an exacerbation could not be assessed. For subjects who discontinue study treatment and remain in the study after the IPD visit, exacerbations will be counted from the time of randomisation up to and including the date of Visit 16 (EOT). Exacerbations that start after Visit 16 (EOT) will not be included in the efficacy assessments but will be listed. If a subject misses Visit 16 (EOT), then any exacerbations that start after the scheduled Visit 16 (EOT) date will be excluded from efficacy assessments. If an exacerbation is ongoing at Visit 16 (EOT), the exacerbation will be counted in the calculation of annual exacerbation rate, however the maximum follow-up time will be truncated at

the date of Visit 16 (EOT), as will the duration of exacerbation. For the subjects who died during the treatment period the exacerbation data collected up to the date of death will be included in the statistical analysis.

The number of days that the subject experiences an exacerbation during the follow-up time, including the subsequent 7 days (when a further exacerbation would not be considered a separate event (and if within the follow-up time)) will be subtracted from the maximum follow-up time to give the maximum time at risk of exacerbation.

In the primary analysis, the number of COPD exacerbations experienced by a subject during their follow-up time will be used as response variable.

The on-treatment annual exacerbation rate will be calculated similarly, as sensitivity analysis, using exacerbations occurring during the on-treatment period as defined in Section 2.1.5. The same formula for annual exacerbation rate will be used for all the estimands in Section 4.2.4.1, and for the corresponding sensitivity analysis in Appendix 8.2.

3.2.1.2 Additional supportive endpoint to primary

The annual rate of moderate or severe COPD exacerbations, excluding those moderate exacerbations treated only with antibiotics, will be used as a supportive endpoint for the primary endpoint. It will be derived similarly to the primary endpoint in Section 3.2.1.1, and includes all severe COPD exacerbations and moderate COPD exacerbations treated by oral corticosteroids (OCS) with or without antibiotics.

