Background (maintenance) COPD medication (ICS/LABA/LAMA)	Allowed	Documented treatment with medium or high dose ICS at a total daily dose corresponding to >250µg fluticasone propionate dry powder formulation equivalent and a LABA and LAMA for COPD throughout the year prior to enrolment (Visit 1) and throughout the study. The dose of ICS should be stable 3 months prior to V1 and throughout the study. See inclusion criterion 7. ICS in a separate, single device is permitted if all the following criteria are met: - it is administered at the same dose and schedule as in the fixed dose combination product; - it is not given in combination with a LAMA alone. If an Investigator decides to switch a subject who is on an ICS in a separate single device to a fixed-dose combination device therapy, this should be done at Visit 1 and the ICS component must remain at the same dose and schedule as used in the 3 months prior to Visit 1 (provided dose and regimen are locally approved for COPD). Nebulized budesonide is accepted as part of maintenance therapy if the dosing regimen is equivalent to that of budesonide approved as part of a combination product for COPD (e.g., for budesonide/formoterol combination 320mcg/9mcg BID equivalent dose of nebulized budesonide is 0.5mg BID [GOLD 2019]

Medication	Allowed/ Restricted/ Prohibited	Details
		Nebulized LABA is accepted as part of maintenance therapy.
		Twice daily triple inhaled (ICS/LABA/LAMA) medications should be withheld at least 12 hours prior to scheduled spirometry at site.
		Once daily triple inhaled (ICS/LABA/LAMA) medications should be withheld at least 24 hours prior to scheduled spirometry at site
		Twice daily LABA or LAMA-containing therapies should be withheld for at least 12 hours prior to scheduled spirometry at site.
		Once daily LABA or LAMA-containing therapies should be withheld for at least 24 hours prior to scheduled spirometry at site.
Additional ICS on top of COPD ICS maintenance medication	Restricted	Can only be given concomitantly with systemic steroids during acute COPD exacerbation treatment while at site or other health care provider. Additional use of ICS outside of this is not allowed.
Systemic corticosteroids (tablets or injections)	Restricted	Prohibited as maintenance treatment within 3 months prior to Visit 1 and throughout the study. Allowed to treat a COPD exacerbation or an AE where there is no alternative treatment available, for no more than 14 days.

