8.1.1.1 Severity of COPD Exacerbations

All protocol defined COPD exacerbations need to fulfil the symptom criteria as defined in Section 8.1.1.

A COPD exacerbation will be considered **severe** if it results in at least 1 of the following:

- Hospitalization defined as inpatient admission for ≥ 24 hours to an observation area, the emergency department, or other equivalent healthcare facility (depending on the country and healthcare system) for the COPD exacerbation
- Death related to COPD or COPD exacerbation

A COPD exacerbation that does not meet the requirements to be classified as severe will be considered **moderate** if it results in at least 1 of the following:

- Use of systemic corticosteroids and/or antibiotics for at least 3 days
- A single depot injectable dose of corticosteroids, which will be considered equivalent to at least 3-day course of systemic corticosteroids

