For subjects who prematurely discontinue treatment, efforts will be made to continue collecting the exacerbation data until the scheduled Visit 16/EOT at Week 52 after randomization. In the statistical analysis of exacerbation rate for the primary estimand, the data collected up to Visit 16/EOT will be included for the patients who prematurely discontinue treatment according to the intent-to-treat principle. For the patients who died during the treatment period the exacerbation data collected up to the date of death will be included in the statistical analysis.

If the cause of any death is related to COPD or a COPD exacerbation, the event will also be included in the rate calculation as a severe exacerbation.

To examine the sensitivity of results of the primary analysis to the underlying assumptions, sensitivity analyses may be performed using different assumptions for missing data following study withdrawal. Further details will be given in the SAP.

The annual rate of moderate or severe COPD exacerbations, excluding those moderate exacerbations treated only with antibiotics, will be used as a supportive endpoint for the primary endpoint. This supportive endpoint includes all severe COPD exacerbations and moderate COPD exacerbations treated by OCS with or without antibiotics.

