GINA	Global Initiative for Asthma
GLI	Global Lung Function Initiative
GMP	Good Manufacturing Practice
GOLD	Global Initiative for Chronic Obstructive Lung Disease
Hb	Hemoglobin
HCG	Human chorionic gonadotropin
НСР	Healthcare practitioner
HFA	Hydrofluoroalkane
Hg	Mercury
HIPAA	Health Insurance Portability and Accountability Act
HIV-1/2	Human immunodeficiency virus-1/2
HL	Hy's Law
HRU	Healthcare resource utilization
IATA	International Air Transport Association
ICH	International Conference on Harmonization

Abbreviation or special term	Explanation
ICI	International Co-ordinating Investigator (If a study is conducted in several countries the International Co-ordinating Investigator is the Investigator coordinating the Investigators and/or activities internationally).
ICF	Informed Consent Form
ICS	Inhaled Corticosteroids
IDMC	Independent data monitoring committee
IEC	Independent ethics committees
IFU	Instructions for Use
Ig	Immunoglobulin
IHC	Immunohistochemistry
IL-5	Interleukin-5
IL-13	Interleukin-13
IL-25	Interleukin-25
IL-33	Interleukin-33
ILC2	Type 2 Innate Lymphoid Cells
IMP	Investigational Medicinal Product
IND	Investigation New Drug (application)
IP	Investigational Product
IPD	Investigational Product Discontinuation
IRB	Institutional Review Board
ISF	Investigator Site File
IUD	Intrauterine device
IUS	Intrauterine system
ITT	Intent-to-Treat
IV	Intravenous
IWRS	Interactive Web Response System
LABA	Long-Acting β2-Agonist
LAMA	Long-Acting Muscarinic Antagonists

Abbreviation or special term	Explanation
LRTI	Low Respiratory Tract Infection
LTRA	Leukotriene Receptor Antagonists
LSLV	Last Subject Last Visit
LTOT	Long term oxygen therapy
mAb	Monoclonal Antibody
MACE	Major Adverse Cardiac Events
MCV	Mean corpuscular volume
MedDRA	Medical Dictionary for Regulatory Activities
MCID	Minimum Clinically Important Difference
mmHg	Millimeter of mercury
MMRM	Mixed effect Model Repeated Measures
MRI	Magnetic Resonance Imaging
mRNA	Messenger Ribonucleic Acid
nAb	Neutralizing Antibodies
NIMP	Non- Investigational Medicinal Product
NIPPV	Noninvasive positive-pressure ventilation
O_2	Oxygen
OAE	Other Significant Adverse Event
OCS	Oral Corticosteroids
PD	Pharmacodynamic
PGx	Genetic research
PHL	Potential Hy's Law
PI	Principal Investigator
PK	Pharmacokinetic(s)
PNV	Predicted Normal Value
PRN	Pro Re Nata (as needed)
PRO	Patient Reported Outcome
PT	Preferred Term

Abbreviation or special term	Explanation
Q4W	Every 4 Weeks
R	Randomization
RBC	Red blood cell
RNA	Ribonucleic Acid

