1.1 Study objectives

1.1.1 Primary objective

Primary Objective	Outcome Measure
To evaluate the effect of tezepelumab as compared with placebo on Chronic Obstructive Pulmonary Disease (COPD) exacerbations in subjects with moderate to very severe COPD	
Primary endpoint: Rate of moderate or severe COPD exacerbations
 
Primary outcome measure: Moderate or severe COPD exacerbation rate ratio (tezepelumab vs placebo)
 
Supportive endpoint: Rate of moderate (excluding exacerbations treated only with antibiotics) or severe COPD exacerbations
 
Supportive measure: Moderate (excluding exacerbations treated only with antibiotics) or severe COPD exacerbation rate ratio (tezepelumab vs placebo)

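### The supportive version of the primary endpoint is defined by two rules that disagree on moderate exacerbations treated with injected but no oral corticosteroid

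*SAP*

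**What the plan says.** Both documents describe the supportive endpoint in two steps.

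- **Exclusion rule.** SAP 3.2.1.2 takes the annual rate of moderate or severe exacerbations, "excluding those moderate exacerbations treated only with antibiotics, will be used as a supportive endpoint for the primary endpoint". Protocol 9.4.2.1 opens in the same way.
- **Inclusion sentence.** The SAP then says that the endpoint is derived like the primary one and "includes all severe COPD exacerbations and moderate COPD exacerbations treated by oral corticosteroids (OCS) with or without antibiotics". The protocol has: "This supportive endpoint includes all severe COPD exacerbations and moderate COPD exacerbations treated by OCS with or without antibiotics".

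The SAP spells out 'oral', and protocol Appendix H expands OCS as "Oral Corticosteroids".

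The definition of a moderate event is wider than oral treatment. One route to it is "Use of systemic corticosteroids and/or antibiotics for at least 3 days" (SAP 3.2.1.1). The other is "A single depot injectable dose of corticosteroids, which will be considered equivalent to at least 3-day course of systemic corticosteroids" (protocol 8.1.1.1, repeated in SAP 3.2.1.1). Protocol Table 6 treats systemic corticosteroids as covering tablets and injections alike.

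Everywhere else, the supportive endpoint is stated by exclusion only. The objectives give "Rate of moderate (excluding exacerbations treated only with antibiotics) or severe COPD exacerbations" (SAP 1.1.1, matching protocol section 3). SAP 4.2.4.1 repeats the primary model without moderate events treated by antibiotics alone. The supportive row of the SAP 8.3 estimand table also excludes antibiotic-only events, but does not limit that exclusion to moderate ones.

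**The concern.** The supportive analysis is there to answer one question: does the treatment effect look the same once antibiotic-only events are set aside? That requires removing those events and no others. A moderate event treated with a depot injection is not antibiotic-only, yet the inclusion sentence does not cover it.

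SAP section 3.2 is where efficacy variables are derived, so it is a natural source for programming. Nothing says which of the two rules governs. Two careful programmers could therefore produce different event counts for the same endpoint. Under the literal inclusion sentence, some steroid-treated events would also be removed because of their route. A difference from the primary result could then no longer be put down to antibiotic-only events.

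**Working it through.** The documents give no event count, rate or power for the supportive endpoint, so there is no figure to reproduce. The check is to apply both rules to every treatment pattern.

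**Set-up.** Each event is coded yes/no on four features: severe, oral steroid, injected steroid, antibiotics. A treatment counts as present only if it qualifies under the exacerbation definition, which means at least 3 days, or one dose for a depot injection. That gives 2^4 = 16 patterns. One of them, not severe with no treatment, is not an exacerbation under the moderate or severe definitions. 15 remain: 8 severe and 7 moderate.

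**Rules.**
- Exclusion rule: keep if severe, or if moderate and not antibiotics-only.
- Inclusion sentence read literally: keep if severe, or if moderate with oral steroid.

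Both rules keep all 8 severe patterns. The 7 moderate patterns are:

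| Oral steroid | Injected steroid | Antibiotics | Exclusion rule | Inclusion sentence |
|---|---|---|---|---|
| no | no | yes | out | out |
| no | yes | no | **in** | **out** |
| no | yes | yes | **in** | **out** |
| yes | no | no | in | in |
| yes | no | yes | in | in |
| yes | yes | no | in | in |
| yes | yes | yes | in | in |

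The rules disagree on 2 of 15 patterns: moderate, injected steroid and no oral steroid, without or with antibiotics.

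**After the change.** If 'oral' becomes 'systemic', the inclusion sentence keeps a moderate event when oral or injected steroid is present. Every moderate pattern has at least one of the three treatments, so this is the same as not antibiotics-only. The rules then agree on 15 of 15.

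**SAP 8.3.** Read literally, its exclusion also removes a severe event treated with antibiotics and no steroid. SAP 3.2.1.2 keeps all severe events. That is a separate disagreement, on 1 of 15 patterns.

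**Number of events.** The share of primary-endpoint events lost would be (share that are moderate) x (share of moderate events with injected but no oral steroid). The documents give neither factor.

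**The case against.** The strongest reply is that the inclusion sentence is only a gloss. It says what the endpoint includes, not that it includes nothing else. It follows an explicit definition by exclusion, and in the SAP it sits beside an instruction to derive the endpoint like the primary one, where depot injections count. The model is specified in SAP 4.2.4.1, which has no oral-steroid condition. The protocol also uses 'oral' loosely elsewhere: section 6.5.4 speaks of prolonged oral corticosteroid treatment when discussing exacerbations in general, and section 8.1.5 names oral corticosteroids as one example of exacerbation treatment.

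Much of this stands. A reader might infer that the inclusion sentence is the operative rule and that events will in fact be dropped. The documents do not support that: no section gives the sentence precedence, and the weight of the text favours the exclusion rule. Loss of events follows only from literal programming of the second sentence.

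The reply does not remove the inconsistency. The sentence sits inside the derivation section, the SAP writes the word 'oral' in full, and both documents separately provide for depot injections, including a stop-date rule. If it is only a gloss, it is an incorrect one. The sponsor has made this kind of correction before: the version 4.0 history in protocol Appendix K records replacing 'oral' by 'systemic' in the COPDCompEx definition.

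**Conclusion.** The two statements in SAP 3.2.1.2 and protocol 9.4.2.1 are not equivalent and should be reconciled. The affected group is moderate events with a depot injection, or at least 3 days of other injected systemic steroid, and no oral steroid. Its size is unknown. The primary endpoint, sample size and success criterion do not change. Under SAP 4.1.2 the supportive p-value is nominal. The correction is worth making because it is specific and cheap, not because the trial's conclusion depends on it.

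Several stronger readings are tempting but go beyond the documents:

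- *All injected-steroid events are at risk.* Severe events, and moderate events that also had an oral course, are kept under both rules.
- *Any intramuscular or intravenous dose given in an emergency visit is affected.* A non-depot injection needs at least 3 days to qualify. A single such dose with no other qualifying treatment is not a primary-endpoint event to begin with.
- *A given percentage of events is lost, more in some countries.* The documents contain no data on steroid route, overall or by region.
- *The treatment comparison is biased.* The trial is double-blind and randomisation is stratified by region; nothing in the documents points to unequal loss between arms.
- *This is the only check on the primary result.* It is the one analysis labelled supportive, but there are also a supplemental estimand, missing-data sensitivity analyses, subgroup analyses and COVID-period analyses.

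**What to change.** 1. In SAP 3.2.1.2 and protocol 9.4.2.1, replace the reference to oral corticosteroids with 'systemic corticosteroids (including a single depot injection)'. Alternatively, delete the inclusion sentence and let the exclusion rule stand alone.
2. Programme the endpoint as primary-endpoint events minus moderate events whose only qualifying treatment is antibiotics. This needs no information on steroid route. That matters because the documents do not state that route is recorded for exacerbation treatment: protocol 6.5 asks for reason and dates, and route is named only for COVID-19 vaccines in section 8.2.10.
3. In the supportive row of SAP 8.3, attach 'moderate' to the exclusion, so that a severe event treated only with antibiotics is kept.
4. If the protocol is not amended again, record the clarification in SAP section 6, which now reports no changes from the protocol, before the primary database lock.

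The cost is one phrase in each of two places, one word in a table and one programming condition. No new data and no new sample size calculation are needed.
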